6.5 LABORATORY TESTS

Patients' HbA1C and Fasting Blood Glucose values will be listed for 14 visits for the patient group receiving the "Approved Treatment Regimen" and for all visits to which the patients attend for the group receiving the "Wait and Extend" treatment regimen, together with the descriptive statistics (n, mean, standard deviation, minimum, median, maximum and 95% confidence interval).

6.6 ASSESSMENT OF RENAL FUNCTION

Patients' Urea, Creatinine, Albumin, Total Protein and Uric Acid values will be collected at the first and fifth visits for patient groups receiving the "Approved Treatment Regimen" and "Wait and Extend" treatment regimen, and will be listed together with the descriptive statistics (n, mean, standard deviation, minimum, median, maximum and 95% confidence interval) for both visits for both treatment regimens.

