6.5.1 Vital signs

Vital signs include BP and pulse measurements. After the patient has been sitting for five minutes, with back supported and both feet placed on the floor, systolic and diastolic blood pressure will be measured three times using an automated validated device, e.g. OMRON, with an appropriately sized cuff. The repeat sitting measurements will be made at 1 - 2 minute intervals and the mean of the three measurements will be used. In case the cuff sizes available are not large enough for the patient's arm circumference, a sphygmomanometer with an appropriately sized cuff may be used.

Vital signs will be evaluated at each visit and will be evaluated after the study injections if applicable.

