6.5.3 Laboratory evaluations

The routine laboratory assessments will be performed at all visits for clinical chemistry and for renal function parameters the assessments will be performed at Baseline/Visit 1, Month 3/Visit 5 and Month 12/Visit 14. The specimens will be obtained for the following assessments:

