9.5 Analysis of secondary variables

9.5.1 Efficacy variables

- Mean change in CRT (μm) by Optical coherence tomography at 12th month from baseline
- Mean no. of injections over a 12-month treatment period
- Mean no. of visits over a 12-month treatment period
- Proportion of patients who gained ≥ 0 , ≥ 5 , ≥ 10 and ≥ 15 letters in BCVA at 12th month
- Incidence of adverse events (AEs) and serious AEs (SAEs), by ophthalmic examinations and IOP measurements, and by changes in vital signs and laboratory parameters over the 12-month assessment period.
- Mean change in VFQ25 scores at 12th month from baseline

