9.5.2 Safety variables

All safety evaluations will be summarized and submitted for each visit per treatment arm.

All adverse events will be summarized per treatment arm, as patient numbers and per cents for any adverse event experience and adverse events for each system organ class will be summarized. All information collected (i.e.: severity or grade or causality assessment) will be summarized. Deaths and SAEs requiring early discontinuation will be summarized separately.

Laboratory details will be submitted as the descriptive statistics of the core data and for changes in the baseline data for each treatment arm (mean, median, standard deviation, interval) will be analyzed by highlighting the clinically notable changes.

Vital signs will be summarized and descriptive statistics will be given for heart rate and pulse in a sitting posture including the baseline changes.

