6.4 VITAL FINDINGS

Patients’ height (cm) and weight (kg) measurements will be tabulated providing descriptive statistics (n, mean, standard deviation, minimum, median, maximum and 95% confidence interval). Body Mass Index will also be calculated from height and weight variables using the Height / (Weight)² formula, and will be described again using descriptive statistics.

Systolic and Diastolic Blood Pressure (mm/Hg) measurements taken in the sitting position will be listed together with descriptive statistics.

These evaluations will be performed for 14 visits for the patient group receiving the “Approved Treatment Regimen” and for all visits to which the patients attend for the group receiving the “Wait and Extend” treatment regimen.

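### The SAP's safety analyses are narrower than the protocol's: no month-12 renal summary, no laboratory or vital-sign change from baseline, no pulse, and none of the three adverse event summaries

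*SAP*

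**What the plan says.** **Renal function.** Protocol 6.5.3 states that "for renal function parameters the assessments will be performed at Baseline/Visit 1, Month 3/Visit 5 and Month 12/Visit 14", and the visit schedule in Protocol 6 also marks three renal assessments, the last at the end of the trial. SAP 6.6 reads "Uric Acid values will be collected at the first and fifth visits" and then gives descriptive statistics for those two visits in each arm.

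**Change from baseline.** Protocol 9.5.1 lists among its variables "changes in vital signs and laboratory parameters over the 12-month assessment period". For laboratory data, Protocol 9.5.2 asks for descriptive statistics of the values and "for changes in the baseline data for each treatment arm", and says these "will be analyzed by highlighting the clinically notable changes". SAP 6.5 (HbA1c and fasting glucose) and SAP 6.6 (renal) plan statistics on the values at each visit and do not mention change.

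**Vital signs.** Protocol 6.5.1: "Vital signs include BP and pulse measurements". Protocol 9.5.2: "Vital signs will be summarized and descriptive statistics will be given for heart rate and pulse in a sitting posture including the baseline changes". SAP 6.4 covers height, weight, BMI and blood pressure. Of blood pressure it says that "measurements taken in the sitting position will be listed together with descriptive statistics". Neither pulse nor change from baseline appears.

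**Adverse events.** Protocol 9.5.2 calls for patient numbers and percentages in each arm, a summary by system organ class, and a separate summary of deaths and of SAEs that led to early discontinuation. SAP 6.15.1 plans a list by visit, and an examination of events by visit, severity, relationship, outcome, action taken and hospital stay.

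**BMI.** SAP 6.4 prints the formula as height divided by weight squared. Protocol 6.5.2 names the two measurements but gives no formula.

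**The concern.** Safety of the injections is a secondary objective in both documents. SAP section 2 gives the plan's purpose as setting out the tables, listings, summaries and graphs to be produced and the methods to be used. A safety output that the protocol requires and the SAP does not name is therefore absent from the document that the programmer works from.

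The renal rule is the most consequential, because it is more than silence. The SAP states a narrower visit list than the protocol. Followed literally, it leaves out the end-of-study values, which are the only renal measurement taken after month 3 and so the only one that reflects the extended part of treatment. The adverse event gap matters because comparing the safety of two regimens needs frequencies by arm, and a list by visit does not give them. Visit numbers in the wait-and-extend arm vary with response, so visits do not line up between arms.

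**Working it through.** The plan gives no figure to reproduce here. The check sets the requirements beside the SAP and counts.

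1. **Renal time points.** Protocol 6.5.3: Visit 1, Visit 5 (month 3) and month 12, which is 3. SAP 6.6: first and fifth visits, which is 2. Missing: 3 − 2 = 1, the month-12 assessment. Protocol 6.5.3 supplies the time point; Protocol 9.5.2 makes it a reporting requirement through its general rule that safety evaluations are summarised for each visit and arm.

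2. **Laboratory change from baseline.** Parameters: HbA1c and fasting glucose (2) plus urea, creatinine, albumin, total protein and uric acid (5), which is 7. Change is required by arm in Protocol 9.5.2 and planned for 0 of 7 in SAP 6.5 and 6.6. This is unlikely to be shorthand. Where the SAP wants change or a first-to-last comparison, it says so: BCVA in 6.9 and 6.14.1, angiography findings in 6.12, retinal thickness in 6.14.2 and VFQ-25 in 6.14.4.

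3. **Vital signs.** Measured under Protocol 6.5.1: blood pressure and pulse, 2. Summarised under SAP 6.4: blood pressure, 1. Missing: pulse. Change from baseline is planned for neither. The two have different support. Protocol 9.5.2 attaches baseline changes to heart rate and pulse and does not name blood pressure there. For blood pressure, change rests on the variable listed in Protocol 9.5.1.

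4. **Adverse event summaries.** Named in Protocol 9.5.2: 3 (counts and percentages by arm; system organ class; deaths and SAEs leading to early discontinuation). Named in SAP 6.15.1: 0. No other SAP section supplies them. The SAP does specify counts and percentages by group elsewhere, for example for ECG (6.7) and concomitant medication (6.13).

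5. **BMI.** The documents give no patient values, so assume 170 cm and 80 kg. As printed, in the SAP's units: 170 / 80² = 170 / 6400 = 0.027. Weight over height squared: 80 / 1.70² = 80 / 2.89 = 27.7. Over an assumed 150–190 cm and 50–110 kg, the printed formula runs from 150 / 110² = 0.012 to 190 / 50² = 0.076. The usual one runs from 50 / 1.90² = 13.9 to 110 / 1.50² = 48.9. The two ranges do not overlap.

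6. **Source document.** SAP section 2 cites protocol IMM-11-0003; the protocol supplied is CRFB002DTR01.

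**The case against.** The strongest reply is that Protocol 9.5.2 still stands. It already specifies the laboratory changes and the adverse event summaries. These are descriptive, with no test attached, and a programmer who reads both documents would produce them. That stands in large part. The adverse event gap alone would be little more than missing detail. It does not answer the renal rule, which gives a shorter visit list, or the BMI formula, which is wrong as printed.

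A reader might infer more than the documents support:

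- *That the SAP cancels the month-12 renal sample.* It speaks of collection at two visits, but the schedule is set by the protocol, which keeps the sample. The gap is in reporting.
- *That the SAP departs from the protocol's grading by using mild, moderate and severe.* Protocol 7.1 uses those same terms, plus life-threatening, where no CTCAE grade exists, and Protocol 9.5.2 accepts either severity or grade.
- *That the SAP's short outcome and action lists lose events.* They may mirror the CRF, which is not among the documents, and Protocol 7.1 offers its actions as examples of how an event may be treated. One check is worth making: that a fatal outcome can be shown.
- *That an open-label study could shape these tables after seeing the data.* Mean change and counts by system organ class leave little room for that, and the protocol already fixes them.
- *That the different protocol number means the SAP belongs to another trial.* Its title, objectives, arms and sample size match this protocol. The number only shows that the reference needs confirming.

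**Conclusion.** The SAP's stated safety analyses fall short of the protocol's and should be aligned before analysis. By count: 1 of 3 renal time points has no planned summary; change from baseline is planned for 0 of 7 laboratory parameters; pulse, 1 of the 2 vital signs measured, is absent together with its change; blood pressure change is absent, though the protocol's call for it is less explicit; and 0 of 3 adverse event summaries are named. The BMI formula is a separate erratum in a descriptive variable, and its results would look absurd at first output.

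The likely consequence is missing tables, with the end-of-study renal values the most important. Nothing here bears on the primary BCVA analysis, the sample size or the significance level. The conclusion rests on the current text of both documents and on the SAP being intended for this version of the protocol. Only the BMI illustration uses assumed values.

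**What to change.** - **First**, confirm which protocol and version the SAP was written against, and correct the citation in SAP section 2.
- **SAP 6.6:** add the month-12 or end-of-trial renal assessment. Define it by time, because visit numbers vary in the wait-and-extend arm.
- **SAP 6.5 and 6.6:** add change from baseline by arm for all seven parameters, and flag clinically notable changes using the ranges that Protocol 7.1 places in Appendix 1.
- **SAP 6.4:** add pulse with its change from baseline, and blood pressure change on the basis of Protocol 9.5.1. Correct BMI to weight (kg) / height (m)².
- **SAP 6.15.1:** name the three Protocol 9.5.2 summaries. Events are already MedDRA-coded (Protocol 8.3), and deaths can be taken from the Study Completion and Death/Survival CRFs named in Protocol 7.1. Check against the CRF that a fatal outcome can be shown.

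The cost is SAP wording and a few extra descriptive tables. The renal samples, pulse readings and event data are already scheduled, so no visit, measurement or treatment rule changes.

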6.7 ECG RESULTS

For both treatment groups, the number and percentage (n and %) of patients with normal and abnormal ECG results will be tabulated.

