6.5.4 Electrocardiogram (ECG)

A standard 12 lead ECG will be performed at Screening/Visit 1 and at the end of study or premature discontinuation visit. Interpretation of the tracing must be made by a qualified physician and documented on the ECG section of the CRF. Each ECG tracing should be labeled with the study and subject number, date, and kept in the source documents at the study site. Clinically significant abnormalities should also be recorded on the Medical History/Adverse event CRF page. Clinically significant findings must be discussed with the Novartis Medical Monitor prior to enrolling the patient in the study.

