7.1 Adverse events

An adverse event (AE) is any untoward medical occurrence (i.e., any unfavorable and unintended sign [including abnormal laboratory findings], symptom or disease) in a subject or clinical investigation subject *after providing written informed consent* for participation in the study. Therefore, an AE may or may not be temporally or causally associated with the use of a medicinal (investigational) product.

The occurrence of adverse events should be sought by non-directive questioning of the patient at each visit during the study. Adverse events also may be detected when they are volunteered by the patient during or between visits or through physical examination, laboratory test, or other assessments.

Abnormal laboratory values or test results constitute adverse events only if they fulfill at least one of the following criteria:

- they induce clinical signs or symptoms,
- they are considered clinically significant,
- they require therapy.

Clinically significant abnormal laboratory values or test results should be identified through a review of values outside of normal ranges/clinically notable ranges, significant changes from baseline or the previous visit, or values which are considered to be non-typical in patient with underlying disease. Investigators have the responsibility for managing the safety of individual patient and identifying adverse events. Alert ranges for labs and other test abnormalities are included in Appendix 1.

Adverse events should be recorded in the Adverse Events CRF under the signs, symptoms or diagnosis associated with them accompanied by the following information.

- the CTCAE grade

If CTCAE grading does not exist for an adverse event, use 1=mild, 2=moderate, 3=severe, and 4=life-threatening. CTCAE Grade 5 (death) is not used, but is collected in other CRFs (Study Completion, Death/Survival).

- its relationship to the study treatment (no/yes)
- its duration (start and end dates) or if the event is ongoing an outcome of not recovered/not resolved should be reported.
- whether it constitutes a serious adverse event (SAE)
- action taken regarding study treatment
- whether other medication or therapies have been taken (concomitant medication/non-drug therapy)
- its outcome (not recovered/not resolved; recovered/resolved; recovering/resolving, recovered/resolved with sequelae; fatal; or unknown)

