6.8 GENERAL OPHTHALMOLOGIC EXAMINATION

6.8.1 Biomicroscopic Evaluation

Frequency and percentage values for the right and left eyes evaluated using biomicroscopy will be listed for 14 visits for the patient group receiving the "Approved Treatment Regimen" and for all available visits for the patient group receiving the "Wait and Extend" treatment regimen. Lids, conjunctiva, cornea, iris, lens, anterior chamber and other assessments will be presented as percentage and frequency values for normal and abnormal assessments for both treatment arms and for both visits.

Frequency and percentage values for the right and left eyes evaluated using ophthalmoscopy will be listed for 14 visits for the patient group receiving the "Approved Treatment Regimen" and for all available visits for the patient group receiving the "Wait and Extend" treatment regimen.

The list of abnormalities identified with color fundus photography will be provided.

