6.12 FLUORESCEIN FUNDUS ANGIOGRAPHY (FFA)

For the results of FFA performed compulsorily at the first and month 12 visits and at investigator discretion during other visits, answers describing presence of diabetic macular edema (Yes, No) will be individually listed as frequency (n) and percentage (%) values for the right and left eyes in each of the treatment arms, and frequency (n) and percentage (%) values for the specified “Focal” and “Diffuse” options will be listed for those with the “Yes” answer. Yes and No answers to macular ischemia and peripheral ischemia questions will be individually listed as frequency (n) and percentage (%) values for the right and left eyes in each of the treatment arms. For Yes, No and Suspected answers to another condition identified with FFA, frequency (n) and percentage (%) values will be tabulated, and the details provided for the Yes answers will be provided.

The rates of diabetic macular edema, macular ischemia, peripheral ischemia and other conditions identified with FFA will be compared during the first and month 12 visits using the Mc Nemar test.

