6.15 SAFETY ASSESSMENT

6.15.1 Adverse / Serious Adverse Events

The list of the Adverse / Serious Adverse Events (SAE) reported in each visit will be provided. All adverse events will be examined regarding the visits they occurred, severity (mild, moderate, severe), relationship with the drug (suspected, not suspected), outcome (continuing, resolved), actions taken (no action taken, dose adjusted/dosing interrupted, additional treatment given, non-pharmacological treatment given, hospitalized), additional treatments if applicable, time between hospitalization and discharge dates, and length of hospital stay.

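### The planned ECG table counts normal and abnormal results per arm without pairing the two ECGs, so it cannot show how many patients became abnormal on study

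*SAP*

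**What the plan says.** Protocol 6.5.4 sets two ECG time points per patient: "A standard 12 lead ECG will be performed at Screening/Visit 1 and at the end of study or premature discontinuation visit". A qualified physician reads each tracing and documents it on the ECG section of the CRF.

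SAP 6.7 is a single sentence: "For both treatment groups, the number and percentage (n and %) of patients with normal and abnormal ECG results will be tabulated". It names no visit, no change from screening and no cross-tabulation. Protocol 9.5.2 supplies the visit dimension in general terms: "All safety evaluations will be summarized and submitted for each visit per treatment arm". Neither document plans a comparison of a patient's final ECG with the same patient's screening ECG.

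Important ECG findings have a second route. Protocol 6.5.4 adds: "Clinically significant abnormalities should also be recorded on the Medical History/Adverse event CRF page". Protocol 7.1 limits which findings count as adverse events: "Abnormal laboratory values or test results constitute adverse events only if they fulfill at least one of the following criteria". The criteria are that the finding causes signs or symptoms, is clinically significant, or needs therapy. SAP 6.15.1 then says: "All adverse events will be examined regarding the visits they occurred".

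**The concern.** The second ECG is useful mainly for showing what changed while the patient was on study. Two sets of totals answer that only in net terms. A patient who goes from normal to abnormal and another who goes from abnormal to normal cancel out. Two regimens could have identical totals at both visits and different numbers of new abnormalities, and the planned table would look the same for both.

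At stake is one descriptive safety result in a trial that lists safety among its secondary objectives and compares two regimens. The primary analysis, the sample size and the capture of adverse events are unaffected.

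**Working it through.** The plan states no ECG figure, so there is nothing to reproduce. The check is on what the planned totals can and cannot determine.

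**Inputs**
- Two ECGs per patient (Protocol 6.5.4).
- Output: normal and abnormal counts per arm (SAP 6.7), taken at each visit (Protocol 9.5.2).
- N = 43 per arm, the evaluable number in Protocol 9.7 and SAP 5.1, taken here as patients with both ECGs.
- The abnormal counts are assumed, because the documents give none.

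**Formulas.** Let a0 be the number abnormal at screening, a1 the number abnormal at the end, and r the number abnormal at screening who are normal at the end.
- Net change = a1 − a0.
- Newly abnormal = a1 − (a0 − r).
- Denominator for new abnormalities = N − a0.
- The totals reveal a0 and a1 but not r. The newly abnormal count can therefore lie anywhere from max(0, a1 − a0) to min(N − a0, a1).

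**Results.** Both examples have a net change of +4.

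| a0 → a1 (of 43) | r | Newly abnormal | Normal at screening | % |
|---|---|---|---|---|
| 9 → 13 | 0 | 13 − 9 = 4 | 34 | 11.8 |
| 9 → 13 | 3 | 13 − 6 = 7 | 34 | 20.6 |
| 9 → 13 | 6 | 13 − 3 = 10 | 34 | 29.4 |
| 9 → 13 | 9 | 13 − 0 = 13 | 34 | 38.2 |
| 4 → 8 | 0 | 8 − 4 = 4 | 39 | 10.3 |
| 4 → 8 | 1 | 8 − 3 = 5 | 39 | 12.8 |
| 4 → 8 | 2 | 8 − 2 = 6 | 39 | 15.4 |
| 4 → 8 | 4 | 8 − 0 = 8 | 39 | 20.5 |

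The last row of each block is the extreme in which every abnormal ECG becomes normal. With 10 of 43 abnormal at both visits, the net change is 0, yet the newly abnormal count can be anything from 0 to 10.

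As a comparison of regimens, suppose both arms go from 9 to 13 of 43, with r = 0 in one and r = 6 in the other. The planned table shows identical arms. The newly abnormal counts are 4 and 10 of 34.

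**Missing second ECGs.** The calculation assumes complete pairs. The sample size section allows for 20% drop-out. The ECG at premature discontinuation offsets this in part, but where a second ECG is missing the two totals rest on different patients, and even the net change is no longer exact.

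**Practice elsewhere in the SAP.** It is mixed. Biomicroscopy (6.8.1) is unpaired, like the ECG: its findings "will be presented as percentage and frequency values for normal and abnormal assessments for both treatment arms and for both visits". Angiographic findings (6.12), which are also yes/no, are paired: their rates "will be compared during the first and month 12 visits using the Mc Nemar test".

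**The case against.** The strongest case against is that nothing in the plan is contradicted. Neither document promises a count of new ECG abnormalities. The ECG is absent from the list of safety assessments in the synopsis and in Protocol 6.5, and 9.5.2 asks for change from baseline for laboratory values and vital signs but not for ECG. Clinically significant changes reach the adverse event tables. Both arms receive the same drug at the same dose. The paired example, angiography, is listed as an efficacy assessment, and the nearest safety analogue, biomicroscopy, is unpaired as well. The illustrative rates are assumed, and the larger ones need most abnormal ECGs to normalise. A shift table could also be produced later from the same data.

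Much of this stands, and it is why the point is minor. There is no inconsistency to correct, the true size of the loss is unknown, and if few ECGs normalise the by-visit totals are close to the truth.

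It does not remove the point. The ECG has its own subsection under the protocol's Safety heading and is repeated at the end of study. The adverse event route leaves out new abnormalities that meet none of the criteria in 7.1. A table that could be made later is not a planned one, and its denominator would then be chosen after the data are seen. Crediting SAP 6.7 with the net change is already generous, because the section names no visit.

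**Conclusion.** The concern holds as a minor improvement to a descriptive safety table. The planned output cannot give the number of patients per regimen who were normal at screening and abnormal at the end. At best it gives the net change and a lower bound. The loss is confined mainly to new abnormalities not judged clinically significant.

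This rests on reading SAP 6.7 together with Protocol 9.5.2; on its own, 6.7 guarantees less. The figures assume 43 patients per arm with both ECGs and invented abnormality counts, so they show that the ambiguity exists and not how large it will be.

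**What to change.** In SAP 6.7, replace the present table with a shift table for each arm. Rows are the screening ECG (normal, abnormal). Columns are the ECG at end of study or premature discontinuation (normal, abnormal, missing). Below it, report n and % newly abnormal, with patients who were normal at screening and have a second ECG as the denominator. No hypothesis test is needed.

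The cost is one table shell. Both ECGs are already recorded on the CRF, so the change needs no protocol amendment and no extra procedure, visit or patient.
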